5.5.3 Withdrawal of Study Participants

Trial participants are free to withdraw from the trial at any point or can be withdrawn by the investigator. If withdrawal occurs, the primary reason for withdrawal should be documented in the participant's Case Report Form (CRF). Trial participant withdrawals will not be replaced.

If a participant discontinues study drug this does not necessarily constitute withdrawal. In this case all attempts should be made to follow up the participant as per protocol and/or re-commencing treatment (if discontinuation was due to adverse events which have subsequently resolved. Refer to section 10). It is important that all patients (with the exception of those that are withdrawn from the trial) undertake the final MRI scan at 96 weeks.

The IDMC can request trial or trial arm suspension/termination, according to the terms of the IDMC charter, for example unacceptable adverse events.

Sponsor No.12/0219 v7 Page **37** of **73**

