6.4 DOSE MODIFICATION AND STOPPING RULES

The following terms will be used:

MS-SMART Version 7 4th June 2018

- 'Full dose' 1 capsule TWICE a day.
- 'Half dose' 1 capsule ONCE a day.
- 'Zero dose' 0 capsules taken.

As the trial is blinded, participants will not know which treatment they are on.

At Baseline:

Participants will be prescribed the 'half dose' for the first 4 weeks.

At 4 Weeks:

Participants will up-titrate to 'full dose' for the remainder of the study.

Dose Modification (if required) – Baseline to Week 4:

If a participant cannot tolerate the 'half dose' (duration according to the Investigator's discretion) the dose should be stopped ('zero dose'). The participant will be re-challenged 2-4 weeks later with the 'half dose' at the discretion of the PI. The participant should then take the 'half dose' for 4 weeks before up-titrating to the 'full dose'.

If however, the participant cannot tolerate the 'half dose' when re-challenged (duration according to local PI discretion), the participant should be off medication for the remaining duration of the trial. The participant will remain in trial follow-up.

Dose Modification as a result of Adverse Events:

At the discretion of the local PI the participant can down-titrate to 'half dose' if Adverse Events (AEs) occur. This does not preclude the participant increasing the dose subsequently (up to the week 24 visit) to the 'full dose'.

If a participant cannot tolerate the 'half dose' (duration according to the Investigator's discretion) the dose should be stopped ('zero dose'). The participant can be re-challenged 2-4 weeks later with the 'half dose' at the discretion of the PI. If they cannot tolerate the 'half dose' again (duration according to local PI discretion) the participant should be off medication for the remaining duration of the trial. The participant will remain in trial follow-up.

If a participant cannot tolerate the 'full dose' (duration according to the Investigator's discretion), the dose should be reduced to 'half dose'. The participant will be re-challenged at 2-4 weeks later. If they cannot tolerate the 'full dose' again (duration according to local PI discretion), they should reduce to 'half dose'. The participant will be re-challenged a second time 2-4 weeks later with the full dose. If the participant cannot tolerate that dose again (duration according to the Investigator's discretion) they should reduce to the half dose for the remaining duration of the trial.

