6.5 PARTICIPANT COMPLIANCE

At each visit participants will bring back the used and unused study drug and will be asked about compliance. Participants will be asked to detail drug compliance over the past 30 days using a diary card to record the number of capsules taken and to indicate any reason for non-compliance. Compliance will be assessed according to the diary card however a pill count will also take place. This information will be collected on the CRF.

Non-compliance to the protocol study procedures will be documented by the investigator and reported to the sponsor as required in section 14.2. Persistent non-compliance may lead the participant to be withdrawn from the study. Follow up as per the protocol will be attempted for all non-compliant participants.

Primary analyses will be intention-to-treat (ITT) using a dataset of all randomized participants, irrespective of treatment actually taken. A complete case approach will be taken for missing data in analysis of each outcome. Participants will be considered compliant with treatment if they reported taking, on average, at least 90% of their prescribed medication in the 30 days preceding each visit.

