7.2 STUDY ASSESSMENTS

The Schedule of Events below provides details of all assessments.

	MS-SMAF	RT Sche	dule of E	Events										
MC CMADTClinic Visit Number	0		1	2	3	4	5	6	7	8		9		
Version 6 5 th October 2017 Visit Type	Screening	Baseline MRI Visit	Baseline	Titration							End of Study MRI {must be done while on IMP]	End of study	Follow- up (Tel.)	Unscheduled visit
			Wk 0	Wk 4	Wk 8	Wk 12	Wk 24	Wk 36	Wk 48	Wk 72	Wk 96	Wk 96	Wk 100	
Window				+/- 1wks	+/- 1wks	+/- 1wks	+/- 2wks	+/- 2wks	+/- 2wks	+/- 2wks		+2 weeks	+/- 4 days	
Informed consent	x													
Inclusion/exclusion criteria review	x		х											
Demography	x													
Review of medical and MS History	x													x
EDSS - Review [Treating physician]	x													
EDSS – [Assessing physician]			х						х			x		
Physical Examination	x								x			x		x
Vital signs	x								x			x		x
Safety bloods CR&E, FBC, LFT (inc.GammaGT)†	x			x	x	x	x	x	x	x		x		xd
Urine pregnancy test†		ха	ха				xa,e					xa,e		
Book MRI	x					х				х				
Core MRI		xb					х				xc			
Compliance assessment				x	x	х	х	x	х	х		x		
Relapse assessment (count / grade)	x		x	x	x	х	x	x	x	x		x		x
Adverse events			х	x	x	x	x	x	x	x		x	x	x
Concomitant Medication	x		х	x	x	х	x	х	х	x		x		x
Randomisation			х											
Prescription issued			xf	x	x	х	х	x	х	х				
Drug up-titration				x										
Follow-up													х	
Blinding Questionnaire												x		
MSFC (9HTP, 25TFW, PASAT)			х						х			x		
SDMT			х						х			x		
SLCVA			х						x			x		

MSIS-29v2		x			x		х	
MSWSv2		x			х		x	
NFI - PRO		x			х		x	
NPRS, NPS and BPI		х			х		х	
EQ-5D		х			х		х	
BDI	х							

Clinic Visit Number	0		1	2	3	4	5	6	7	8		9		
Visit Type	Screening	Baseline MRI Visit	Baseline	Titration							End of study MRI	End of study	Follow- up (Tel.)	Unsheduled visit
			Wk 0	Wk 4	Wk 8	Wk 12	Wk 24	Wk 36	Wk 48	Wk 72		Wk 96	Wk 100	
Window				+/- 1wks	+/- 1wks	+/- 1wks	+/- 2wks	+/- 2wks	+/- 2wks	+/- 2wks		+2wks	+/- 4 days	
OCT (subgroup)			xg									xc		
CSF Neurofilament/lymphocytes (subgroup) Lumbar puncture††			xg						x			хс		
CSF Neurofilament/lymphocytes (subgroup) Blood & urine samples††			xg			x	x		x	x		хс		
Advanced MRI (subgroup)		x										х		x
Staff Present														x
Treating Neurologist	у								у			у		x
Independent Assessing Neurologist			У						у			у		
Study Nurse	у		у	у	У	у	У	у	у	у		у		xd

Notes				
a= must occur prior to MRI and at baseline visit, within 1 week (-7 days) Applies to WOCBP. Repeat testing will be dependent on timing of assessments.				

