b= must occur before baseline visit				
c= must occur within 7 days prior to the final clinic visit or at the final clinic visit (visit 9)				
d= at PI discretion				
e= pregnancy test prior to MRI (within 7 days prior)				
f= Prescription after randomisation				
g= Must occur before or on day of baseline visit (i.e. procedures conducted before trial treatment commences)				
+ Samples processed at local site laboratories				
++ samples processed at central laboratory				

Screening Visit (Visit 0):

Screening (- 30 days)

Patients will be identified as indicated above (see section 5.1 for further clarification) and if deemed suitable to enter the trial will be informed about the trial and provided with a patient information leaflet. They will be asked to contact the co-ordinating centre if they would like to attend for a screening assessment or the recruiting centre will contact the patient to arrange a screening assessment.

At the screening visit, patients will have further opportunities to discuss the trial with members of the clinical team and if they wish to proceed, will provide written, *informed consent*.

The following will be assessed and recorded:

- inclusion/exclusion criteria
- demography
- review of medical and MS history
- review EDSS [treating physician]
- physical examination
- vital signs
- safety bloods (Cr&E,FBC, Hb, LFT inc. ^γGT)
- relapse assessment (count and grade)
- concomitant medication
- BDI-II

Anticipated visit duration = 60 minutes

If any of the safety bloods are clinically significant (CS), they can be repeated at Baseline and the repeat safety blood result(s) at Baseline will be used to assess eligibility.

If a patient is ineligible at Screening (apart from CS safety bloods), they can be re-screened (where appropriate) after a minimum period of 1 month.

Core Brain MRI (Completed by Week 0)

WOCBP will have a urine pregnancy test within 7 days prior to their MRI, compliant with National Guidelines for MRI.

Sub-studies (Completed by Week 0)

Those participants who have consented to additional MRI imaging (advanced MRI) will have this procedure at the time of the baseline MRI visit. Participants taking part in CSF neurofilament and CSF lymphocyte phenotyping testing (lumbar puncture, blood and urine) &/or Optical Coherence Tomography (OCT) will have these procedures completed either before the baseline visit or during the baseline visit (before trial treatment commences).

Visit Number 1:

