9.1 SAMPLE SIZE CALCULATION

9.1.1 Primary MRI Outcome, PBVC

A total of 440 patients will be randomised equally (1:1:1:1) between the three active treatments and the placebo to give 110 per treatment arm. The primary analysis will be intention-to-treat (ITT) on the whole study cohort (n=110/arm). Based on two UK phase II trials (Lamotrigine ⁶⁰ and MS-STAT ²⁷), we expect 10% of the total cohort to drop out of the trial before Year 2, and a further 10% of the total cohort to come for their Year 2 visit, but be off medication. Thus we anticipate 90 patients per arm completing the study.

From the calculations reported in by Altmann et al ⁴³ for measurement of PBVC using the SIENA registration-based method, and further data provided by [name] summarised in the table below (Table A), 90 patients per arm would give over 90% power to detect a 40% reduction in PBVC on any active arm compared to placebo and 80% power to detect a 35% reduction (Bonferroni adjustment for multiple comparisons of three 1.67% two-sided tests, giving 5% overall two-sided significance level). While these sample sizes are based on annual measurement time points and comparison of mean rates of change using longitudinal linear mixed models, Altmann et al also confirm that they are almost identical to the sample size requirements under analysis of covariance of PBVC adjusting for baseline value, the proposed method of analysis in this trial.⁴³

MRI measurement tir	Baseline, 96 weeks						
2-sided significance	0.0167		0.05				
Statistical power		80%	90%	80%	90%		
Treatment effect	30%	123	158	92	123		
	35%	90	116	68	91		
	40%	69	89	52	70		

Table A - Required sample size per arm by treatment effect size, significance level and statistical power; treatment effect expressed as relative mean difference in PBVC under treatment. PBVC assessed using SIENA registration-based method.

For a more exploratory analysis without adjusting for multiple comparisons, this sample size will give almost 90% power to detect a 35% reduction in atrophy. The study is not powered to detect differences between the three active treatment arms.

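### The on-drug label on the week-96 scan and the non-compliance withdrawal clause conflict with the protocol's ITT analysis and put the primary data set at risk

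*Protocol*

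**What the plan says.** The statements that bear on who has the week-96 scan, all in the Protocol:

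- **7.2, Schedule of Events, first panel:** the column for the primary scan is headed "End of Study MRI {must be done while on IMP". The second panel heads the same column without that condition. The footnote on the week-96 core MRI concerns timing only: "c= must occur within 7 days prior to the final clinic visit or at the final clinic visit (visit 9".
- **5.5.3:** "If a participant discontinues study drug this does not necessarily constitute withdrawal", and "It is important that all patients (with the exception of those that are withdrawn from the trial) undertake the final MRI scan at 96 weeks".
- **6.4:** of patients who are off medication for good after a failed re-challenge, "The participant will remain in trial follow-up".
- **6.5:** the primary analyses are ITT on all randomised participants, whatever treatment they took. The same section says "A complete case approach will be taken for missing data in analysis of each outcome" and "Persistent non-compliance may lead the participant to be withdrawn from the study", and adds that follow-up of all non-compliers will be attempted.
- **9.1.1:** "The primary analysis will be intention-to-treat (ITT) on the whole study cohort (n=110/arm". It expects 10% to drop out before Year 2 and a further 10% to attend off medication, leaving 90 per arm completing.
- **9.2.2:** patients with baseline and 96-week brain volume are analysed as randomised, irrespective of treatment received.

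**The concern.** A patient who has stopped drug cannot meet the label, so a site following it literally would not scan someone whom 5.5.3 and 9.2.2 require to be scanned and analysed.

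The second route does not depend on the label. A patient withdrawn from the study for non-compliance is exempt from the final scan under 5.5.3. That patient then drops out of an analysis that needs both scans, although 6.5 describes the set as all randomised participants. Section 6.5 gives no criterion for when non-compliance is persistent.

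Stopping drug and poor compliance occur after randomisation and may depend on the arm. The protocol itself cites liver enzyme rises leading to withdrawal in 4% of a riluzole group (1.2.2.2) and names hyperkalaemia as the main issue with amiloride (1.2.2.3). If such patients go unscanned at different rates by arm and also differ in atrophy, the primary comparison is no longer protected by randomisation. A scan not taken at week 96 cannot be recovered.

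**Working it through.** **Inputs (9.1.1).** 110 randomised per arm; 10% drop-out; a further 10% attending off medication; 90 completers; 1.67% two-sided per comparison; Table A. The protocol gives no SD for PBVC, so the SD/mean ratio *c* is backed out of Table A.

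**1. Reproduce the plan's figure.** With *e* the relative reduction, n per arm = 2(c/e)²(z₁₋α/₂ + z₁₋β)². Solving the twelve cells gives c = 0.725 to 0.730, mean 0.727. For a 35% reduction at 80% power: 2 × (0.727/0.35)² × (2.393 + 0.842)² = 90.3, against 90 stated. All twelve cells reproduce within one patient. Power at 90 per arm is 79.9% for a 35% reduction and 90.3% for 40%, as stated. Because c comes from the same table, this checks internal consistency only.

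**2. Who the 90 are.**
- All attenders at Year 2: 110 × 0.9 = 99.
- Attenders still on drug: 110 × 0.8 = 88.
- Difference: 11 per arm, 44 in all, or 11/99 = 11% of attenders.

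The stated 90 is close to 88 and not to 99. The power section therefore appears to set aside the off-drug attenders whom 5.5.3 and 9.2.2 keep.

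**3. Power on each reading (1.67% level).**
- 88 per arm, on drug only: 78.8% for a 35% reduction, 89.6% for 40%.
- 99 per arm, effect undiluted: 84.0% and 93.0%.
- 99 per arm, assuming no effect in the 11 off drug: the reductions become 35% × 88/99 = 31.1% and 40% × 88/99 = 35.6%, with power 73.2% and 85.3%.

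**4. Possible bias if off-drug attenders go unscanned.** Take a true effect of nil. Let f be the off-drug share of the 99 attenders in each arm, and let off-drug patients' PBVC be k SD worse in both arms. The f split and k are assumptions; the protocol gives neither by arm.

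Bias in SD units: b = (f_active − f_placebo) × k. As a share of the placebo mean: b × 0.727. SE = √(1/n_active + 1/n_placebo), with n the number still scanned. Two-sided error = P(|Z + b/SE| > 2.393).

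| Off drug of 99, active vs placebo | k = 0.25 | k = 0.5 | k = 1 |
|---|---|---|---|
| 11 vs 11 | 0; 1.67% | 0; 1.67% | 0; 1.67% |
| 15 vs 7 | 1.5%; 1.8% | 2.9%; 2.1% | 5.9%; 3.3% |
| 11 vs 0 | 2.0%; 1.9% | 4.0%; 2.5% | 8.1%; 5.2% |

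Each cell gives the bias as a share of the placebo mean, then the error rate. Example, 11 vs 0 with k = 1: b = 0.111; 0.111 × 0.727 = 8.1%; SE = √(1/88 + 1/99) = 0.147; b/SE = 0.76; error 5.2%.

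Withdrawal for non-compliance cannot be sized in the same way, because the protocol gives no expected number.

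**The case against.** The label may be no more than a timing instruction. Footnote c places the scan at visit 9 or in the 7 days before it, visit 9 has a window of +2 weeks, participants finish medication there, and 14.6 stops drug after the final assessment. On that reading sites are being told to scan before the drug ends, and nothing states that an off-drug patient is not scanned. The second schedule panel carries no condition. The governing text in 5.5.3, 6.4 and 9.2.2 retains off-drug patients. Withdrawal for non-compliance is optional, and the next sentence of 6.5 promises attempted follow-up. Section 9.2.1 compares missing week-96 scans by arm. The bias figures rest on assumed splits and prognosis, and the direction could reverse.

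Most of this stands. A reader might infer that the label and the clause turn the ITT analysis into an on-treatment or selected comparison. The documents do not support that, because the analysis text says otherwise in several places. What survives is that the label does not say it is only about timing, that footnote c already sets the timing, and that nothing says whether a patient withdrawn for non-compliance is still asked for the scan.

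A reader might also infer that the primary model should be replaced by one that uses the week-24 scan. That does not follow either. Section 9.2.6 leaves missing-data methods and sensitivity analyses to the SAP, so their absence here is no finding. The week-24 scan is there to look for pseudoatrophy (2.2.2.1, 9.2.3.1), so relying on it could carry an early drug artefact into the primary estimate.

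**Conclusion.** The point holds as a contradiction that puts the ITT set at risk; it does not show that the planned analysis is already selected. Taken literally, the label conflicts with 5.5.3, 6.4, 9.1.1 and 9.2.2 on about 11 patients per arm, using the plan's own 10%. The non-compliance clause, together with the scan exemption and the complete-case rule, is a second route to losing randomised patients, and it sits poorly with the claim in 6.5 to analyse all of them.

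The size of any bias cannot be derived from the documents. It is nil if off-drug shares and prognosis are equal across arms, and reaches about 8% of the placebo mean only in the most extreme scenario tried (11 vs 0 off drug, 1 SD worse). That the contradiction exists is certain; its practical effect depends on how sites read the schedule.

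**What to change.** Reconcile the Schedule of Events in 7.2 with 5.5.3, 6.5, 9.1.1 and 9.2.2:

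1. Reword the column heading as timing only: for participants still taking IMP, scan before it ends; all randomised participants who have not withdrawn consent to follow-up are scanned at week 96, on or off IMP. Use the same heading in both panels.
2. In 5.5.3 and 6.5, state that participants withdrawn for non-compliance are still asked for the week-96 MRI unless they withdraw consent. No change to any treatment-stopping rule is proposed.
3. In 9.1.1, say whether the 90 completers are patients scanned or patients scanned and on drug. In 6.5, describe the analysed set as 9.2.2 does.
4. Optionally, add a sensitivity analysis that uses week-24 PBVC for missing week-96 values. Keep the 9.2.2 model as primary.

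The cost is wording and a reminder to sites. Scanning off-drug patients may dilute the effect (step 3 of the check), but the ITT plan already accepts that. The change helps only scans not yet taken, so it should be made before the final scans are done.

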6.3 DOSING REGIME

Following randomisation, study drug will be dispensed by the site pharmacy.

Patients are prescribed 1 capsule a day (OD), orally at baseline. At 1 month they will up-titrate to 1 capsule twice a day (bd) orally for the remainder of the study; no relationship to food is required.

That is:

- Fluoxetine 20 mg twice per day (20 mg once per day for first 4 weeks)
- Riluzole 50 mg twice per day (50 mg once per day for first 4 weeks)
- Amiloride 5 mg twice per day (5 mg once per day for first 4 weeks)
- Placebo –1 capsule twice per day (1 capsule once per day for first 4 weeks)

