6.6.4 Management of laboratory abnormalities

Potassium

- If Potassium <2.8mmol/l or >5.5mmol/l, the medication will be suspended. Repeat Potassium at 2-4 weeks. If Potassium <2.8mmol/l or ≤ 5.5mmol/l continue to monitor, and consider re-challenge. If not suspend for a further 2-4 weeks.
- If Potassium remains <2.8mmol/I or >5.5mmol/I discontinuation of treatment is recommended.

Sodium

- If Sodium <125mmol/l, the medication will be suspended. Repeat Sodium at 2-4 weeks. If Sodium <125mmol/l continue to monitor, and consider re-challenge. If not suspend for a further 2-4 weeks.
- If Sodium remains <125mmol/l discontinuation of treatment is recommended.

Sponsor No.12/0219 v7 Page **42** of **73**

Liver function tests

- If ALT or AST or bilirubin or ^yGT <3 times the ULN, commencement, continuation or advancement of placebo/IMP is reasonable.
- If ALT or AST or bilirubin or [¥]GT >3 times the ULN, confirm by repeat measurement within a week. If abnormalities persist, consider dose reduction to 'half dose' (if taking medication bd, i.e. 'full dose') or stopping medication 'zero dose' (if taking 'half dose'). Repeat parameters at 2-4 weeks. If parameters improve towards baseline, continue to monitor, and consider re-challenge.
- If ALT or AST or bilirubin or ^YGT >5 times the ULN discontinuation of treatment is recommended.

Renal function (creatinine)

- If creatinine >130µmol/l, confirm by repeat measurement within a week. If abnormalities persist, reduce to 'half dose' (if taking medication bd, i.e. 'full dose') or stopping medication 'zero dose' (if taking 'half dose'). Repeat parameters at 2-4 weeks. If parameters return to baseline, continue to monitor, and consider re-challenge.
- If creatinine remains >130µmol/l discontinuation of treatment is recommended.

Full blood count (FBC)

- If neutrophil count reduces to <1.0x10⁹ /I suspend medication. Repeat parameters at 2-4 weeks. If parameters improve towards baseline, continue to monitor, and consider re-challenge. If neutrophil count remains <1.0x10⁹ /I discontinuation of treatment is recommended.
- If platelet count reduces to <50 x10⁹/l suspend medication. Repeat parameters at 2-4 weeks. If parameters improve towards baseline, continue to monitor, and consider re-challenge. If platelet count remains <50 x10⁹/l discontinuation of treatment is recommended.

Haemoglobin (Hb)

If haemoglobin <80g/l suspend medication and commence local protocol for investigating anaemia.

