7 STUDY ASSESSMENTS

7.1 SAFETY ASSESSMENTS

Safety assessments will include the monitoring of Adverse Events and Serious Adverse Events by the Investigator. For more details on Adverse Events please refer to section 10.

Safety Bloods: A blood sample will be taken at screening and routine blood levels will be checked to identify any values which are more than 3 times the upper limit of normal site reference ranges [for LFT] or below acceptable levels [WBC, haemoglobin, lymphocyte, neutrophil, platelet and sodium levels], above acceptable levels [creatinine] or above/below acceptable levels [potassium]. Those patients will not be eligible for trial entry.

A repeat blood sample may be taken at baseline to re-test one or more values out of range as necessary.

Routine safety bloods will be collected at trial assessments and processed at local site laboratories in accordance with local policy and guidelines. Putative Serum biomarkers such as lactate Sponsor No.12/0219 v7

dehydrogenase (LDH) and haptoglobin will be monitored at the UCL site only to monitor progression of the disease.

Women of childbearing potential (WOCBP, defined as women who are not postmenopausal (12 months since last menses or permanently sterilised) will require a negative urine pregnancy test prior to each MRI scan compliant with National Guidelines for MRI and prior to study inclusion (within 7 days of baseline visit). WOCBP will be required to use adequate contraception during the trial.

Safety assessments will include the monitoring of adverse events and serious adverse events by the site investigator. For more details on adverse events please refer to Section 10.

Depression: Patients with a score of 19 or higher on the BDI at the screening visit will not be eligible for trial entry.

CSF Neurofilament and CSF lymphocyte phenotyping **Sub Study** (*This section only applicable to centres participating in this sub-study*):

Those participants on the CSF neurofilament and CSF lymphocyte phenotyping sub study will have consented to this sub study. These samples will be processed in a central laboratory that holds an appropriate licence to hold, process and analyse tissue samples. Details on sample handling, processing, storage and shipment are in the CSF neurofilament and CSF lymphocyte phenotyping Sub study protocol 2.

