Baseline/Randomisation (Week 0)

At baseline, the following assessments will be completed: inclusion/exclusion criteria confirmation EDSS [assessing physician] urinary pregnancy test (within 7 days of baseline visit, where applicable) MS Functional Composite (MSFC: 9HPT,25TFW,PASAT) Symbol Digit Modalities Test (SDMT) Sloan Low contrast visual acuity (SLCVA) Multiple Sclerosis Impact Scale v2 (MSIS29) Multiple Sclerosis Walking Scale v2 (MSWS) NFI NPRS, BPI and NPS Health economic questionnaire (EQ-5D)

> Sponsor No.12/0219 v7 Page **48** of **73**

Repeat safety bloods (if required) patients will be assessed to confirm they have not had a relapse (count/grade) between screening and baseline adverse events concomitant medication

Randomisation will occur once all baseline assessments have been done and the participant has been confirmed as eligible. Trial participants will then receive their baseline (Week 0) drug prescription. Participants will take the 'half dose' for the first 4 weeks, starting treatment the morning after the Baseline/Randomisation visit.

Anticipated visit duration = 60 minutes

Visit Number 2: Week 4 (+/- 1 week) Trial participants return to the research clinic and the following assessments will be completed: safety bloods (Cr&E,FBC, Hb, LFT inc. [¥]GT) compliance assessment relapse assessment (count/grade) adverse events concomitant medication

The dose will be up-titrated to the maximum 'full dose'.

Trial participants will receive their next prescription.

Anticipated visit duration = 20 minutes

Visit Number 3:

Week 8 (+/- 1 week) Trial participants return to the research clinic and the following assessments will be completed: safety bloods (Cr&E,FBC, Hb, LFT inc. [¥]GT) compliance assessment relapse assessment (count/grade) adverse events concomitant medication

Trial participants will receive their next prescription.

Anticipated visit duration = 20 minutes

Visit Number 4: Week 12 (+/- 1 week) Trial participants return to the research clinic and the following assessments will be completed: safety bloods (Cr&E,FBC,Hb, LFT inc. ^γGT) compliance assessment relapse assessment (count/grade) adverse events concomitant medication

The next MRI appointment is booked.

Trial participants will receive their next prescription.

Anticipated visit duration = 20 minutes

Those patients consented to the CSF neurofilament and CSF lymphocyte phenotyping sub study will have their blood and urine sampled +/- 14 days of visit 4.

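### The week-4 dose increase makes no reference to the bloods drawn at that visit, and the liver and creatinine rules do not say which dose they mean

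*Protocol*

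**What the plan says.** **Dose by time.** Section 6.4: "Participants will be prescribed the 'half dose' for the first 4 weeks". Section 6.3: "At 1 month they will up-titrate to 1 capsule twice a day (bd) orally for the remainder of the study". Section 7.2, Visit 2 (week 4): "The dose will be up-titrated to the maximum", meaning one capsule twice a day. None of the three mentions a laboratory result. The exception in 6.4 for the period up to week 4 concerns a participant who cannot tolerate the half dose.

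**Bloods at the same visit.** Visit 2 also lists safety bloods and the next prescription, in a visit expected to take 20 minutes. Section 7.1 has routine samples "processed at local site laboratories in accordance with local policy and guidelines" and gives no turnaround time.

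**Laboratory rules.** Section 6.6.4 says that when liver tests are below 3 x ULN, "commencement, continuation or advancement of placebo/IMP is reasonable". Above 3 x ULN the value is repeated within a week: "If abnormalities persist, consider dose reduction to" half dose if the participant is on full dose, or stopping if on half dose. The creatinine rule (above 130 µmol/l) has the same structure without the word consider.

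**A different liver limit.** The hepatic and renal paragraph of section 1.2.2.1 (fluoxetine) says that treatment is stopped above 3 x ULN, with no repeat and no half-dose step.

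**The concern.** Section 6.6.4 links a liver result to whether the dose may go up; the sections that tell the site to raise the dose do not. A nurse following Visit 2 and a physician following 6.6.4 could act differently on the same participant.

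The liver and creatinine rules then depend on what the participant is taking, and the text does not say whether that means the dose when the sample was drawn or the dose when the result is acted on. Across the week-4 step these are different doses. The action could therefore turn on how fast the laboratory reports, and not on the dose at which the abnormality appeared.

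At stake are consistent safety management between sites and a clear record of why a dose was changed. The primary analysis is by randomised group irrespective of treatment taken (sections 6.5 and 9.2.2), so its definition is unaffected.

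**Working it through.** No power, alpha or event count bears on this point. The check sets the sections side by side.

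**1. Size of the step** (sections 6.1.1 and 6.3). One capsule a day becomes two: fluoxetine 20 to 40 mg/day, riluzole 50 to 100 mg/day, amiloride 5 to 10 mg/day. The factor is 2 in each active arm.

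**2. Week 4 is the first on-treatment sample.** The schedule in 7.2 has safety bloods at screening and then at weeks 4, 8, 12, 24 and later. A baseline repeat is possible, but it precedes the first dose, since participants are described as "starting treatment the morning after the Baseline/Randomisation visit".

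**3. Which rules in 6.6.4 depend on current dose.**

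| Parameter | Action | Depends on current dose? |
|---|---|---|
| Potassium | suspend | no |
| Sodium | suspend | no |
| Neutrophils | suspend | no |
| Platelets | suspend | no |
| Haemoglobin | suspend | no |
| Liver tests above 5 x ULN | discontinuation recommended | no |
| Liver tests above 3 and up to 5 x ULN, persisting on repeat | consider full to half, or half to zero | yes |
| Creatinine above 130 µmol/l, persisting on repeat | full to half, or half to zero | yes |

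There are seven parameter groups, taking liver as one. Five suspend at any dose. Two depend on dose, and liver does so only in its middle band.

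**4. One abnormality, two actions.** Take a week-4 sample, drawn on half dose, that falls under one of the two dose-dependent rules and persists on repeat.

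- *Acted on before the increase:* the participant is taking half dose, so the step is to zero dose (consider, for liver).
- *Acted on after the increase:* the participant is taking full dose, so the step is to half dose, the dose on which the abnormality arose. The confirmatory repeat would have been drawn on full dose.

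In both cases the value is checked again at 2-4 weeks. The difference is half dose or zero dose over that interval, plus time on full dose beforehand.

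**5. Which case is likelier.** Action requires a repeat within a week. Even with a fast first result, that repeat would fall after the increase unless someone held the increase. For liver tests the advancement wording suggests holding it; for creatinine there is no such wording. Visit 2 carries neither condition.

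**6. Section 1.2.2.1 against 6.6.4.** Above 3 x ULN the former stops treatment; the latter repeats and then considers a reduction. The risk-minimisation paragraph of 1.2.2.1 itself refers significant liver changes to the laboratory-abnormalities section (cited there as 6.7.3). Because treatment is blinded, a fluoxetine-only rule could not be applied without unblinding.

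**7. Who is still exposed.** Section 1.2.2.1 states that recruitment is complete. Version 7 is dated 4 June 2018 and the trial is planned to end on 31 October 2018: 149 days, or 149/7 = 21.3 weeks. A participant whose week-100 call falls by that end date was at week 100 - 21.3 = 78.7 or later when version 7 was issued. If the end date covers the last follow-up call, the scheduled week-4 step is past for everyone.

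**The case against.** The strongest reply is that the sections can be read together. Up-titration at week 4 is the default, and 6.4 and 6.6.4 modify it. The advancement wording may only be permissive; if it is a gate, it already qualifies Visit 2. Section 6.4 lets the investigator reduce the dose for adverse events, and section 10.3 records clinically significant laboratory abnormalities as adverse events. This shows that a careful investigator has room to act safely. It does not settle which dose the two rules refer to, and it does not remove the conflict with 1.2.2.1.

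A reader might infer several stronger points that the protocol does not support:

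- *That the 6.6.4 rules in general step back only to the dose that caused the problem.* Most suspend at any dose, and liver tests above 5 x ULN lead to recommended discontinuation.
- *That the dose is always doubled before results exist.* No turnaround is stated, and a same-day result or a held increase is not excluded.
- *That the participant is left on the offending dose.* The liver step is discretionary, values are repeated at 2-4 weeks, bloods are due again at week 8, and creatinine that stays high leads to recommended discontinuation.
- *That the 10% with raised liver tests on riluzole (section 1.2.2.2) measures the problem.* That figure is for 100 mg/day, the full dose, and is tied neither to a 3 x ULN threshold nor to week 4. The same section says that ALT values of 3-5 x ULN usually became normal on continued treatment.
- *That the run-in was meant as a laboratory check.* Section 6.6.4 does not mention it; 6.4 describes it in terms of tolerability.

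**Conclusion.** The point holds in a narrow form. The time-based increase in 6.3, 6.4 and Visit 2 is not reconciled with the liver condition in 6.6.4. Two dose-dependent rules leave their reference dose undefined, so the same half-dose abnormality can lead to half dose or zero dose. Section 1.2.2.1 gives a different liver action again.

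The consequence at week 4 assumes that results are acted on after the increase, which is likely but not stated. The undefined reference dose and the conflict with 1.2.2.1 need no such assumption. The number of participants affected cannot be estimated, because the protocol gives no rate of persistent week-4 abnormalities on half dose. With recruitment complete, what remains is mainly later re-challenge after a laboratory abnormality and an account of how the rules were applied. It is a low-priority clarification and implies no judgement on which titration or stopping rule is right.

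**What to change.** Reconcile sections 1.2.2.1, 6.3, 6.4, 6.6.4 and Visit 2 in 7.2 so that they state consistently:

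1. whether the increase to full dose depends on the week-4 results, and on which of them;
2. in the liver and creatinine rules, whether taking half or full dose means the dose at sampling or the dose when the result is acted on;
3. that the same reading applies to increases after re-challenge;
4. which action applies to liver tests above 3 x ULN, since 1.2.2.1 and 6.6.4 differ.

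The clinical team chooses each rule. The cost is protocol wording. If the increase is made to wait for results, add a telephone call and a few days' delay in reaching full dose. Waiting for the week-4 results needs no extra routine sample or scheduled visit.
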